3.14.3.3. Exocrine Pancreas Safety

3.14.3.3.1. Pancreatic Enzyme

Observed pancreatic enzyme data (p-amylase and lipase) will be summarized by treatment and nominal visit. The counts and percentages of participants with maximum postbaseline pancreatic enzyme value exceeding the following thresholds will be provided by baseline pancreatic enzyme value (less than or equal to the ULN, and greater than the ULN), and treatment: less than or equal to 1 times the ULN, greater than 1 to less than or equal to 3 times the ULN, greater than 3 to less than or equal to 5 times the ULN, greater than 5 to less than or equal to 10 times the ULN, greater than 10 times the ULN.

An MMRM analysis will be used to analyze each pancreatic enzyme with a log transformed (postbaseline measure/baseline measure) response variable and treatment, nominal visit, treatment-by-nominal visit interaction as fixed effects.

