3.14. Safety Analyses

Unless specified otherwise, safety assessments will be based on the SS ([Table GPHR.3.1](#)). All events that occur between the date of first dose of study drug to the date of patient's safety follow-up visit or patient's end of study participation will be included, regardless of the adherence to study drug or availability of the end of treatment liver biopsy. For assessing the benefit and risk profile through 52 weeks, selected safety analyses will be conducted by utilizing safety data from first dose through the date of the 52-week visit.

The statistical assessment of homogeneity of the distribution of categorical safety responses among treatment arms will be conducted using Fisher's exact test, unless specified otherwise.

The mean change from baseline differences among treatments at all scheduled visits will be assessed via an MMRM using REML, unless specified otherwise. The model will include baseline T2DM status (Yes/No), the region (Japan, US including Mexico, and Europe including Israel), treatment group, visit and treatment-by-visit interaction as fixed effects, and baseline value of the safety parameter as a covariate. To model the covariance structure within patients, the unstructured covariance matrix will be used. If this model fails to converge, the covariance structures specified in Section [3.11.2.1](#) will be tested in order.

For selected safety parameters, time-to-first-event analysis via the Cox Proportional-Hazards model may be conducted. Patients without the event will be censored at the end of study participation. For patients experiencing the event, the "time-to-first-event" will be the time (in days) from first dose to first occurrence of the event.

Where necessary, the rate of events will be analyzed using a generalized linear mixed-effects model assuming the number of events follow a negative binomial distribution and with treatment as a fixed effect. The logarithm of days during the active treatment period will be adjusted as an offset to account for possible unequal treatment duration of follow-up between patients.

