3.14.6. Vital Signs

Descriptive summaries by treatment and by nominal visit will be provided for baseline and postbaseline values as well as change from baseline values. If 2 records are taken at the same visit, they will be averaged prior to being used for data summaries and analyses.

An MMRM using REML will be used to fit the changes from baseline in vital signs at all scheduled postbaseline visits. The model will include baseline T2DM status (Yes/No), the region (Japan, US including Mexico, and Europe including Israel), treatment group, visit, and

treatment-by-visit interaction as fixed effects, and baseline value of the dependent variable as a covariate. To model the covariance structure within patients, the unstructured covariance matrix will be used.

Counts and percentages of patients with abnormal sitting systolic BP, sitting diastolic BP, and pulse will be presented by treatment. The criteria for identifying patients with treatment-emergent vital sign abnormalities are stated in [Table GPHR.3.3](#).

Table GPHR.3.3. Categorical Criteria for Abnormal Blood Pressure and Pulse Measurements

Parameter	Low	High
Systolic BP (mm Hg) (supine or sitting - forearm at heart level)	≤ 90 and decrease from baseline ≥ 20	≥ 130 and increase from baseline ≥ 20
Diastolic BP (mm Hg) (supine or sitting - forearm at heart level)	≤ 50 and decrease from baseline ≥ 10	≥ 90 and increase from baseline ≥ 10
Pulse (bpm) (supine or sitting)	< 50 and decrease from baseline ≥ 15	> 100 and increase from baseline ≥ 15

Abbreviation: BP = blood pressure.

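### The pancreatic-enzyme MMRM leaves out the baseline covariate, T2DM status and region that the other two safety MMRMs include, at a modest and avoidable cost in precision

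*SAP*

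**What the plan says.** SAP 3.14 sets a default for continuous safety measures. Mean changes from baseline "will be assessed via an MMRM using REML, unless specified otherwise". On terms it says "The model will include baseline T2DM status (Yes/No), the region (Japan, US including Mexico, and Europe including Israel), treatment group", then visit and "treatment-by-visit interaction as fixed effects, and baseline value of the safety parameter as a covariate".

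SAP 3.14.6 repeats this structure for vital signs: change from baseline as the response, T2DM status, region, treatment and visit in the model, and "treatment-by-visit interaction as fixed effects, and baseline value of the dependent variable as a covariate".

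SAP 3.14.3.3.1 gives the pancreatic enzymes a statement of their own, with the log of the postbaseline-to-baseline ratio as the "response variable and treatment, nominal visit, treatment-by-nominal visit interaction as fixed effects". T2DM status, region and a baseline covariate are not mentioned, and no reason for a shorter model is given.

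SAP 3.14.4 (laboratory) and 3.14.7 (ECG) specify no MMRM of their own, so these are the only three safety MMRMs in the SAP. T2DM status and region are the two randomization strata (SAP 2.3).

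**The concern.** A log ratio is a change score on the log scale. Dividing by baseline is not the same as adjusting for it, because it forces the slope of postbaseline on baseline to be 1. When the true slope is lower, the change score carries baseline noise that a covariate would remove. The SAP recognises this elsewhere: the default and vital-signs models both use a change response and still include baseline.

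The log scale does not explain the difference. Table GPHR.3.2 sends log-transformed ALT, AST and GGT to the MMRM of SAP 3.11.2.1, which includes baseline, T2DM status and region.

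At stake is the precision of the estimated dose effects on p-amylase and lipase. Protocol 8.3.7.2 collects these enzymes in order to assess such effects, and this MMRM is the only model-based analysis named for them. With about 49 participants per arm, some chance imbalance at baseline is to be expected.

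**Working it through.** The plan states no figure for this analysis, so there is none to reproduce. The check compares model terms and then sizes the consequence.

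**Terms side by side**

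| Term | 3.14 default | 3.14.6 vital signs | 3.14.3.3.1 enzymes |
|---|---|---|---|
| Response | change | change | log(post/baseline) |
| Treatment, visit, interaction | yes | yes | yes |
| Baseline covariate | yes | yes | no |
| T2DM status, region | yes | yes | no |

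**Inputs**

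- About 196 randomized 1:1:1:1 (SAP 2.3), so 196/4 = 49 per arm; fewer will remain at later visits.
- Two-sided alpha 0.05 (SAP 3.2).
- Correlation rho between log baseline and log postbaseline enzyme: not in the documents. Assumed 0.5 to 0.95.
- Equal variances at baseline and follow-up, and one postbaseline visit: simplifying assumptions.

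**Precision lost by omitting log baseline**

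With SDs s0 at baseline and s1 at follow-up:

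- Variance of the log ratio: s0² + s1² − 2·rho·s0·s1.
- Residual variance with log baseline as covariate: s1²(1 − rho²).
- Difference: (s0 − rho·s1)², which is never negative. Apart from the degrees of freedom used, adjustment cannot lose precision.
- With s0 = s1, the ratio of adjusted to unadjusted variance is (1 − rho²)/[2(1 − rho)] = (1 + rho)/2.

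The SE inflation is 1/√[(1 + rho)/2] − 1. The last column is the power of the unadjusted model, at 49 per arm, for an effect that would have 80% power when adjusted.

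| rho | Variance ratio | SE inflation | Power unadjusted |
|---|---|---|---|
| 0.5 | 0.750 | 15.5% | 67.9% |
| 0.6 | 0.800 | 11.8% | 70.7% |
| 0.7 | 0.850 | 8.5% | 73.3% |
| 0.8 | 0.900 | 5.4% | 75.7% |
| 0.9 | 0.950 | 2.6% | 78.0% |
| 0.95 | 0.975 | 1.3% | 79.0% |

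**Chance imbalance**

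If arms differ by d in mean log baseline, the expected follow-up difference includes rho·d. The log-ratio contrast then includes rho·d − d = −(1 − rho)d. The SD of d between two arms of 49 is √(2/49) = 0.20 baseline SD. An imbalance of that size shifts the contrast by −0.10 SD at rho 0.5, −0.06 at 0.7, −0.02 at 0.9 and −0.01 at 0.95.

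**Cost of the extra terms**

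They are log baseline (1), T2DM status (1) and region (2), four parameters in all. A simulation of four arms of 49, 4,000 runs per scenario, compared the full model with treatment alone. With strata unrelated to outcome, the variance ratios were 0.73, 0.84, 0.96 and 0.99 at rho 0.5, 0.7, 0.9 and 0.95. These are close to the formula, so the four parameters cost little.

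**Omitted strata**

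Stratified randomization balances T2DM status and region. If they are prognostic, a model without them leaves their variance in the residual and reports too large a standard error. In the simulation T2DM status shifted the follow-up log value by an assumed 0.3 SD. The ratio of reported variances, full model to treatment only, was then 0.74, 0.82, 0.86 and 0.80 at the same four correlations.

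**The case against.** The strongest reply is that 3.14.3.3.1 may be incomplete drafting rather than a reduced model. It names no estimation method or covariance structure, so something must come from 3.14, and the covariates might be meant to come with it. That is possible. But 3.14 counts T2DM status and region among its fixed effects, and 3.14.3.3.1 gives its own list of fixed effects without them. Because 3.14 gives way where another section specifies otherwise, inheritance is not the natural reading. If it was intended, a sentence should say so.

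The reply has more force on consequence, and most of that stands. No hypothesis, decision rule or sample size depends on this model. The threshold tables in the same section are already split by baseline enzyme level. Pancreatitis is assessed from adjudicated and investigator-reported events (SAP 3.14.3.3.2), and protocol 8.3.7.2 itself says that serial enzymes predict acute pancreatitis poorly in asymptomatic patients. SAP 3.2 also permits additional analyses, although that does not change the model stated here.

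Three stronger readings are tempting, and the documents do not support them:

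- That baseline is ignored and any imbalance passes in full into the contrast. Baseline is the denominator of the response, and only a (1 − rho) share passes, with reversed sign.
- That the comparison is biased, or distorted by skewed enzymes. Randomization keeps the unadjusted contrast unbiased on average, and the response is already on the log scale.
- That this section departs from a long run of safety models. There are two others.

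**Conclusion.** The point holds as one of precision and consistency. The stated enzyme model is valid, but it omits a baseline value already collected and both randomization strata, all of which the other two safety MMRMs include.

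The size of the loss depends on a correlation that the documents do not report. Under equal variances at a single visit, the standard error is about 8% to 15% too large at rho 0.5 to 0.7, and only 1% to 3% too large at 0.9 to 0.95. A prognostic stratum would add to the overstatement; how much depends on an effect that the documents do not give. The formula is a one-visit approximation to a repeated-measures model.

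Severity is low. The primary endpoint, sample size and type I error are unaffected.

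**What to change.** In SAP 3.14.3.3.1, add log(baseline enzyme) as a covariate and baseline T2DM status and region as fixed effects. Alternatively, state that the 3.14 default terms apply, with baseline on the log scale. Either wording settles the question of inheritance, and the same sentence can confirm that the REML estimation and covariance fallback of 3.14 apply.

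The cost is one SAP line and about four degrees of freedom. No new data are needed, and the treatment contrasts still back-transform to ratios of geometric means.

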3.14.3.3.2. Pancreatitis Events

Summaries of adjudicated and investigator-reported pancreatic events will be provided by treatment. Detailed searching criteria can be found in Appendix 1 (Section 6.1).

Treatment-emergent, adjudicated pancreatitis will be considered as AESI. Listing of participants with adjudicated pancreatitis may be provided if deemed necessary.

3.14.3.4. Gastrointestinal Safety

3.14.3.4.1. Nausea, Vomiting, and Diarrhea

The time courses of prevalence and incidence (newly occurring episodes) of nausea, vomiting, diarrhea, and combined will be plotted by treatment and maximum severity. The maximum severity and duration of treatment-emergent nausea, vomiting, diarrhea, and combined through the end of the study will be summarized by treatment.

3.14.3.4.2. Severe Gastrointestinal Events

Severe GI AEs (GI SOC) will be captured with AE-CRF form and serious cases will be captured with the SAE form. The PTs in the gastrointestinal SOC will be used to identify GI AEs. The incidence of the resulting TEAEs will be summarized by treatment and PT. PTs with severe/serious cases in the GI SOC will be considered AESIs. The counts and percentages of participants with severe GI events will be summarized by treatment.

3.14.3.5. Thyroid Safety Monitoring

3.14.3.5.1. Calcitonin

Observed calcitonin data will be summarized by treatment and nominal visit. Additionally, the number and proportion of patients with a maximum postbaseline calcitonin value exceeding the following thresholds will be provided by treatment and maximum baseline calcitonin value (less than or equal to 20 ng/L, greater than 20 ng/L): less than or equal to 20 ng/L, greater than 20 ng/L to less than or equal to 35 ng/L, greater than 35 ng/L to less than or equal to 50 ng/L, greater than 50 ng/L to less than or equal to 100 ng/L, greater than 100 ng/L.

3.14.3.5.2. C-Cell Hyperplasia and Thyroid Malignancies

Thyroid malignancies and C-cell hyperplasia will be considered as AESI. Treatment-emergent thyroid malignancies and C-cell hyperplasia will be identified using MedDRA HLT for Thyroid neoplasms and PT for Thyroid C-cell hyperplasia.

The counts and percentages of participants with treatment-emergent thyroid C-cell hyperplasia and malignancies will be summarized by treatment and PT ordered with decreasing frequency. In addition, a listing of participants with treatment-emergent thyroid C-cell hyperplasia and neoplasms may be provided if deemed necessary.

3.14.3.6. Major Adverse Cardiovascular Events (MACE)

MACE reported by investigators are adjudicated by an independent CEC in a blinded fashion.

The MACE of special interest are: deaths due to cardiovascular cause, myocardial infarction, hospitalization for unstable angina, hospitalization for heart failure, coronary interventions (such as coronary artery bypass graft or percutaneous coronary intervention); and cerebrovascular events, including cerebrovascular accident (stroke) and transient ischemic attack.

Only adjudicated MACE will be considered as AESI. The counts and percentages of participants with adjudicated MACE may be summarized by treatment.

A listing of participants reporting MACE events, either reported by investigator or identified by the CEC, will be provided. The listing will include treatment, participants identification including the site number, date of event, type of event as reported by the investigator, type of event as adjudicated by the CEC, time from first dose of study drug to the event, and time from last dose to the event (if participant has discontinued study drug prior to the event).

3.14.3.7. Treatment-Emergent Supraventricular Arrhythmias and Cardiac Conduction Disorders

Treatment-emergent supraventricular arrhythmias and cardiac conduction disorders will be considered as AESI. The cardiovascular events will include clinically relevant rhythm and conduction disorders.

The AE database will be searched using predefined SMQs or MedDRA HLTs to identify events consistent with supraventricular arrhythmias and cardiac conduction disorders. Detailed searching criteria can be found in Appendix 1 (Section 6.1).

The incidences of the resulting TEAE will be summarized by treatment and PT nested within SMQs and HLTs. The PT will be ordered with decreasing frequency within SMQ. A listing of participants with treatment-emergent supraventricular arrhythmias and cardiac conduction disorders may be provided if deemed necessary.

3.14.3.8. Hypersensitivity Reactions

Hypersensitivity events will be considered AESI. Hypersensitivity reactions and related information will be summarized by treatment. Two main analyses are performed:

- **Potential Immediate Hypersensitivity:** Analysis of TEAEs occurring from the start of study drug administration up to 24 hours after the end of study drug administration. For events without the hypersensitivity eCRF, only date (no time) information is collected, and the events occurring on the same date as the study drug injection will be included.
- **Potential Non-Immediate Hypersensitivity:** Analysis of TEAEs occurring more than 24 hours after the end of study drug administration, but prior to subsequent study drug administration.

Summaries of all potential hypersensitivity reactions will be generated by PT with decreasing frequency by treatment. The AE database will be searched using predefined SMQs to identify events consistent with hypersensitivity events. Detailed searching criteria for hypersensitivity events can be found in Appendix 1 (Section 6.1).

3.14.3.9. Injection Site Reactions

ISRs, incidence and rates, and related information reported via the “Injection Site Reactions” eCRF will be summarized by treatment. Information to be summarized includes the location of the reaction, timing of the reaction relative to study drug administration, and characteristics of the ISR: erythema, induration, pain, pruritis, and edema.

Additionally, potential ISRs will be reported by PT within MedDRA HLTs of ISRs, administration site reactions, and infusion-related reactions. The counts and percentages of participants with treatment-emergent ISR will be summarized by treatment using the MedDRA

PTs. Detailed searching criteria for ISR events can be found in Appendix 1 (Section 6.1). The PTs will be used for summary within each HLT category. All ISRs will be considered AESIs.

The counts and percentage of participants with ISRs will be summarized by treatment. A listing of participants with treatment-emergent severe/serious ISRs may be provided, if deemed necessary.

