# 7. Discontinuation of Study Intervention and Participant Discontinuation/Withdrawal

# 7.1. Discontinuation of Study Intervention

Possible reasons leading to permanent discontinuation of investigational product:

- Subject Decision
  - o the participant or the participant's designee (for example, parents or legal guardian) requests to discontinue investigational product.
- Investigator Decision
  - o the investigator decides that the patient should be discontinued from the study medication
- Any medication for weight loss is given for more than 1 week
- Participants will be discontinued from the investigational product in the following circumstances:
  - o Diagnosis of cirrhosis after randomization (refer to Section 8.3.7.1 for details)
  - o Pancreatitis or pancreatic cancer (refer to Section 8.3.7.2 for details)
  - o Diagnosis of MTC after randomization
  - Diagnosis of an active or untreated malignancy (other than basal or squamous cell skin cancer, in situ carcinomas of the cervix, or in situ prostate cancer) after randomization
  - Any severe injection site reaction, or 2 or more moderate injection site reactions occurring a week or more apart
  - o Any significant study drug-related hypersensitivity reaction
  - Any TEAE, SAE, or clinically significant laboratory value for which the investigator believes that permanent study drug discontinuation is the appropriate measure to be taken
  - Any TEAE or SAE considered possibly or probably related to study drug that is severe or medically significant but not immediately life-threatening; or where hospitalization or prolongation of hospitalization is indicated; or is disabling; or limits self-care activities of daily living
  - Any TEAE or SAE regardless of attribution to study drug that has lifethreatening consequences or urgent intervention is indicated
  - o A female participant becomes pregnant
  - o Diagnosis of T1DM or latent autoimmune diabetes in adults
- If the patient develops any exclusion criteria during the course of the study, the investigator should call the sponsor to determine whether discontinuation of study drug is necessary

• Significant non-compliance with the protocol

If study drug is permanently discontinued, the patient should remain in the study if possible. The patient may continue participation in the study, attend all visits, and undergo most protocol procedures.

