# 8.2.4.1. Immunogenicity Assessment

Where local regulations and ERBs allow, blood samples for immunogenicity testing will be collected to determine antibody production against tirzepatide as specified in the SoA (Section 1.3).

At the visits and times specified in the SoA (Section 1.3), venous blood samples will be collected to determine antibody production against tirzepatide. To interpret the results of immunogenicity, a PK sample will be collected at the same time points as the immunogenicity samples in all post-baseline samples to determine the plasma concentrations of tirzepatide. All samples for immunogenicity should be collected predose when applicable and possible.

Additional samples (including ADA, PK, and exploratory immune safety samples) may be collected if there is a possibility that an AE is immunologically mediated (See Section 8.3.7.10) "Hypersensitivity Events"). Instructions for the collection and handling of blood samples will be provided by the sponsor. The actual date and time (24-hour clock time) of each sampling will be recorded. Sample collected at Visit 801 will assess immunogenicity at washout of tirzepatide (5 half-lives post end of treatment).

Treatment-emergent ADA are defined in Section 9.4.6.

A risk-based approach will be used to monitor patients who develop treatment-emergent ADA after treatment with tirzepatide. Clinically significant treatment-emergent ADA will be defined as any treatment-emergent ADA at the follow-up visit (Visit 801) with:

- A high ( $\ge$ 1:1280) or increasing titer at the follow-up visit (V801)
- An association of treatment-emergent ADA with a moderate-to-severe injection site reaction or infusion-related reaction

Patients who are treatment-emergent-ADA positive at the last scheduled assessment or discontinuation visit will have additional samples taken at 3, 6, 9 (optional), and 12 months postlast assessment until the titer returns to within 2-fold of baseline titer or for up to 1 year, whichever is less. Patients followed for at least 1 year since last dose who have not returned to baseline as defined above will be assessed for safety concerns. If no clinical sequelae is recognized by the clinical team, then no further follow-up will be required.

Immunogenicity will be assessed by a validated assay designed to detect and titer ADA in the presence of tirzepatide at a laboratory approved by the sponsor. Samples with detected ADA

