### 8.3.7.11. Injection Site Reactions

All injection site reactions and information regarding their time of day, time relative to injection, size, amount of erythema, induration, and pruritus, as well as severity, will be recorded on specific CRFs. In addition, if the reaction is clinically significant, the site should attempt to contact the sponsor for potential follow-up procedures. Injection site reactions do not need to be recorded as AEs as well unless they meet SAE criteria.

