3.14.1.1. Treatment-Emergent Adverse Events

A TEAE is defined as an event that first occurred or worsened in severity after first dose of study drug. The MedDRA LLT will be used in the treatment-emergent derivation. The maximum severity for each LLT during the baseline period including ongoing medical history will be used as baseline severity. For events with a missing severity during the baseline period, it will be treated as “mild” in severity for determining treatment-emergence. Events with a missing severity during the postbaseline period will be treated as “severe” and treatment-emergence will be determined by comparing to baseline severity.

For events occurring on the day of first taking study medication, the CRF-collected information (e.g., treatment-emergent flag, start time of study treatment and event) will be used to determine whether the event was pre- versus post-treatment, if available. If the relevant information is not available, then the events will be counted as post-treatment.

The counts and percentages of participants with TEAEs will be summarized by treatment using MedDRA PT nested within SOC. Events will be ordered by decreasing frequency within SOC. The SOC will be in alphabetical order. For events that are sex-specific, the denominator and computation of the percentage will include only participants from the given sex.

An overview of the number and percentage of participants who experienced a TEAE, SAE, death, discontinued from study treatment or study due to an AE, relationship to study drug, and outcome of the AE will be summarized by treatment.

The counts and percentages of patients with TEAEs by maximum severity will be summarized by treatment using MedDRA PT. For each participant and TEAE, the maximum severity for the MedDRA PT is the maximum postbaseline severity observed from all associated LLTs mapping to the MedDRA PT. The maximum severity will be determined based on the nonmissing severities. If all severities are missing for the defined postbaseline period of interest, it will show as missing in the table.

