3.14.1.5. Discontinuation Due to Adverse Events

The counts and percentages of participants who discontinued from study treatment or study due to an AE during the postbaseline period may be summarized by treatment group using MedDRA PT nested within SOC. Events will be ordered by decreasing frequency within SOC. In case of discontinuation from study treatment, a time-to-event analysis will be conducted by treatment on time to study drug discontinuation as well as on time to study drug discontinuation due to an AE.

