3.14.5. Immunogenicity

TE ADA are defined as those with a titer 2-fold (1 dilution) greater than the minimum required dilution (1:10) if no ADAs were detected at baseline (treatment-induced ADA) or those with a 4-fold (2 dilutions) increase in titer compared to baseline if ADAs were detected at baseline (treatment-boosted ADA). A patient is evaluable for TE ADA if the patient has a non-missing baseline ADA result, and at least 1 non-missing postbaseline ADA result.

The frequency and percentage of patients with preexisting ADA, with TE ADA, with neutralizing TE ADA, and with cross-reactive TE ADA to tirzepatide will be tabulated by dose, where proportions are relative to the number of patients who are TE ADA evaluable. The frequency and percentage of patients with hypersensitivity and injection site reactions by TE ADA status will be tabulated if warranted by the data.

A listing may be provided of all immunogenicity assessments for those patients who at any time had TE ADA present. This includes the tirzepatide concentration from a simultaneous PK sample, and the clinical interpretation result. A listing may be provided for all participants who had ADAs present at any time (including baseline) or had any hypersensitivity or injection site reaction TEAEs.

Depending on the number of patients with TE ADA, selected efficacy and safety subgroup analyses by TE ADA categories may be performed if deemed necessary. TE ADAs that are associated with AEs of either severe/serious hypersensitivity or severe/serious injection site reaction will be classified as AESI.

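### Several SAP safety outputs rest on AE records, but non-serious injection site reactions need not be recorded as AEs, so those outputs may undercount them by an unknown amount

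*SAP*

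**What the plan says.** **Collection.** Protocol 8.3.7.11 sends every ISR to a dedicated form; details of the reaction, "as well as severity, will be recorded on specific CRFs". It adds: "Injection site reactions do not need to be recorded as AEs as well unless they meet SAE criteria". Two other places point the other way. Protocol 8.3.7 lists ISRs within the allergic/hypersensitivity group of AESIs, and 8.3.7.10 has all allergic or hypersensitivity reactions reported as AEs or SAEs.

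**Stopping drug.** Protocol 7.1 includes among the circumstances for discontinuing study drug: "Any severe injection site reaction, or 2 or more moderate injection site reactions occurring a week or more apart". Neither case has to meet a seriousness criterion.

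**Analysis.** SAP 3.14.3.9 plans two ISR summaries. The first gives incidence, rates and characteristics from the ISR form. The second is additional: "potential ISRs will be reported by PT within MedDRA HLTs of ISRs, administration site reactions, and infusion-related reactions". Its data source is not named. Elsewhere the SAP works from AEs:

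- 3.14.1.1: "The counts and percentages of participants with TEAEs will be summarized by treatment using MedDRA PT nested within SOC", plus a table by maximum severity and an overview that includes discontinuations due to an AE.
- 3.14.1.2: common TEAEs, meaning those in at least 1.0% of participants.
- 3.14.1.5: an optional table of "participants who discontinued from study treatment or study due to an AE during the postbaseline period", and a planned time-to-event analysis of stopping drug because of an AE.
- 3.14.5: "TE ADAs that are associated with AEs of either severe/serious hypersensitivity or severe/serious injection site reaction will be classified as AESI".

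No SAP text says that ISR-form events are coded to MedDRA terms or added to these outputs.

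**The concern.** The form that holds every ISR and the records that feed the general safety tables are different sources, and the rule linking them is permissive. A site that follows 8.3.7.11 can leave a severe but non-serious ISR on the ISR form only. Such an event can then be absent from the TEAE tables and from the severity table. If it led to stopping drug, that stop can be missing from the AE-discontinuation analysis. If the participant also developed treatment-emergent ADA, the event can be missing from the ADA-associated AESI.

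The ISR-form summary does not fully make up for this. The items that SAP 3.14.3.9 names from the form are location, timing and physical characteristics. Severity is collected but is not among them, and the listing of severe or serious ISRs is optional.

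**Working it through.** The plan states no ISR rate or count, so there is no figure to reproduce. The check sets the recording rule against each output.

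| Output | SAP section | Stated basis | ISR-form events brought in? |
|---|---|---|---|
| ISR incidence, rates, characteristics | 3.14.3.9, first summary | ISR form | Yes |
| ISR by PT within HLT | 3.14.3.9, second summary | Not named; AE records by inference | Not stated |
| TEAEs by SOC/PT, maximum severity, overview | 3.14.1.1 | AEs | Not stated |
| Common TEAEs | 3.14.1.2 | AEs | Not stated |
| Discontinuation due to an AE | 3.14.1.1, 3.14.1.5 | AEs | Not stated |
| ADA-associated ISR AESI | 3.14.5 | AEs | Not stated |

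The inference in the second row rests on two facts. Protocol 9.4.4 mentions MedDRA coding only for adverse events, and the search criteria sit in an appendix whose title refers to adverse events of special interest.

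**Illustration of size.** The only input from the documents is the planned arm size: 196 / 4 = 49. Three quantities are assumptions:

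- I: the share of participants with an ISR
- s: the share of those that are serious
- v: the share of non-serious ISRs that sites enter as AEs anyway

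Expected participants per arm in the ISR-form summary = 49 × I.

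Expected participants per arm in an AE-based table = 49 × I × [s + (1 − s) × v].

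With I = 10% and s = 2%, the form summary expects 49 × 0.10 = 4.9. The AE-based table expects:

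- v = 0: 4.9 × 0.02 = 0.1
- v = 25%: 4.9 × (0.02 + 0.98 × 0.25) = 4.9 × 0.265 = 1.3
- v = 50%: 4.9 × (0.02 + 0.98 × 0.50) = 4.9 × 0.51 = 2.5
- v = 100%: 4.9 × 1 = 4.9

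Over I = 2% to 20% and s = 0 to 5%, the AE-based count runs from 0 to 49 × 0.20 × 0.05 = 0.49 at v = 0. At v = 100% it equals the form count, from 49 × 0.02 = 0.98 to 49 × 0.20 = 9.8. The result turns almost entirely on v, which the documents do not fix and which may differ between sites.

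**The case against.** The strongest reply has five parts.

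1. **ISR incidence comes from the ISR form, and all ISRs are AESIs.** This stands. A reader might infer that the report will lose the ISR rate; SAP 3.14.3.9 shows otherwise. The PT/HLT table is a supplement, so a count that differs from the form's is not in itself a contradiction.
2. **The AE source of the PT/HLT table is not stated.** This stands. SAP 3.14.3.7, 3.14.3.8 and 3.14.3.11 say that the AE database will be searched; 3.14.3.9 does not, and the content of Appendix 1 was not available for this check. The inference is reasonable, but it remains an inference. It does not affect 3.14.1 or 3.14.5, where AEs or TEAEs are named.
3. **The rule excuses AE entry but does not forbid it, and 8.3.7 with 8.3.7.10 can be read as requiring it.** This stands against any claim that the AE-based tables will show almost no ISRs. It does not cure the problem: if sites read the rules differently, AE entry depends on the site.
4. **Other outputs cover part of the gap.** SAP 3.7 and 3.9.1 summarise study drug disposition and reasons for stopping, and 3.14.5 plans ISRs by ADA status if the data warrant it. This stands in part. The stop itself stays visible, but its attribution to an ISR in the AE-discontinuation analysis does not follow, and the ADA tabulation is conditional.
5. **Keeping dedicated-form events out of the AE records is a deliberate design.** It is, and SAP 3.14.3.1 uses it for hypoglycemia. There, though, the SAP restates the recording rule, names the form and says how to avoid double counting. For ISRs it names the form for the first summary only, and does none of this for the added table.

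**Conclusion.** The mismatch is real and worth correcting. As written, the TEAE, common-TEAE, severity and AE-discontinuation outputs, the ADA-associated ISR AESI and, by inference, the ISR PT/HLT table may undercount non-serious ISRs. That includes severe ones that lead to stopping drug. The amount is unknown and possibly site-dependent: from nearly all of them missing to none missing. For overall TEAEs only the ISR contribution is at risk. The counts under working illustrate this range and rest on assumed rates.

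Two stronger readings go beyond the documents. One is that the understatement is larger on tirzepatide than on placebo; no ISR rate by arm is given. The other is that SAP 3.14.5 uses the wrong severity level because protocol 8.2.4.1 refers to "An association of treatment-emergent ADA with a moderate-to-severe injection site reaction or infusion-related reaction". That passage defines clinically significant treatment-emergent ADA at the follow-up visit, for monitoring patients. The SAP sentence classifies a reporting category, so the two need not share a threshold.

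**What to change.** - **SAP 3.14.5:** identify severe or serious ISRs for the ADA-associated AESI from the ISR form as well as from AE records.
- **SAP 3.14.1 and 3.14.3.9:** name the source of each table. Code ISR-form events to MedDRA PT, then merge and de-duplicate them with AE records for the ISR PT/HLT, TEAE, severity and AE-discontinuation tables. Alternatively, show the TEAE tables with and without ISR-form events.
- **Drug stops:** use the ISR form to attribute a discontinuation to an ISR where no AE was entered.
- **Protocol:** reconcile 8.3.7.11 with 8.3.7 and 8.3.7.10, so that sites have one recording rule for ISRs.

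The SAP changes use ISR data that the protocol already collects. The cost is some coding and programming, and slightly higher TEAE percentages. One point to confirm first: the fields that the documents list for the ISR form are characteristics of the reaction, and no verbatim term is mentioned, so the SAP should say how a form entry is assigned a PT.
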